11.4.3 Expectedness

[name], the PI, and [name], the Co-investigator, will be responsible for determining whether an adverse event (AE) is expected or unexpected. An AE will be considered unexpected if the nature, severity, or frequency of the event is not consistent with the risk information previously described for the study intervention.

11.5 Adverse Event and Serious Adverse Event Reporting

11.5.1 Adverse Event Reporting

From the time of treatment allocation through **90** days following cessation of treatment, all adverse events, that begin or worsen after informed consent, **must be recorded** by the investigator or designee at each examination on the Adverse Event case report forms/worksheets.

The investigator will make every attempt to follow all subjects with non-serious adverse events for outcome.

Conditions that were already present at the time of informed consent should be recorded in the Medical History page of the patient's CRF/worksheet.

Adverse events will be assessed and graded according to the Common Terminology Criteria for Adverse Events (CTCAE) version 5.0. Grade 1 to 5 will be used to characterize the severity of the Adverse Event.

If CTCAE grading does not exist for an adverse event, the severity of mild, moderate, severe, and life-threatening, death related to the AE corresponding respectively to Grades 1 - 5, will be used. Information about any deaths (related to an Adverse Event or not) will also be collected through a Death form (or EOT/SEC/Survival Information in NOVDD). The occurrence of adverse events should be sought by non-directive questioning of the patient (patient) during the screening process after signing informed consent and at each visit during the study. Adverse events also may be detected when they are volunteered by the patient (patient) during the screening process or between visits, or through physical examination, laboratory test, or other assessments. As far as possible, each adverse event should be evaluated to determine:

1. The severity grade (CTCAE Grade 1-5)
2. Its duration (Start and end dates)
3. Its relationship to the study treatment (Reasonable possibility that AE is related: No, Yes) or Its relationship to the study treatment (Reasonable possibility that AE is related: No, Yes, investigational treatment, Yes, the study treatment (non-investigational), Yes, both and/or indistinguishable)
4. Action taken with respect to study or investigational treatment (none, dose adjusted, temporarily interrupted, permanently discontinued, unknown, not applicable)
5. Whether medication or therapy was given (no concomitant medication/non-drug therapy, concomitant medication/non-drug therapy)
6. Whether it is serious, where a serious adverse event (SAE) is defined as in Section 9.2 and which seriousness criteria have been met (include for NCDS trials)

Outcome (not recovered/not resolved, recovered/resolved, recovering/resolving, recovered/resolved with sequelae, fatal, unknown)

If the event worsens the event should be reported a second time in the CRF noting the start date when the event worsens in toxicity. For grade 3 and 4 adverse events only, if improvement to a lower grade is determined a new entry for this event should be reported in the CRF noting the start date when the event improved from having been Grade 3 or Grade 4. For phase I studies any AE

that constitutes a DLT should be reported like a grade 3 and 4 adverse event. All adverse events should be treated appropriately. If a concomitant medication or non-drug therapy is given, this action should be recorded on the Adverse Event CRF.

Once an adverse event is detected, it should be followed until its resolution or until it is judged to be permanent, and assessment should be made at each visit (or more frequently, if necessary) of any changes in severity, the suspected relationship to the study treatment, the interventions required to treat it, and the outcome. Progression of malignancy (including fatal outcomes), if documented by use of appropriate method (for example, as per RECIST criteria for solid tumors), should not be reported as a serious adverse event.

Adverse events separate from the progression of malignancy (example, deep vein thrombosis at the time of progression or hemoptysis concurrent with finding of disease progression) will be reported as per usual guidelines used for such events with proper attribution regarding relatedness to the drug.

Laboratory abnormalities that constitute an Adverse event in their own right (are considered clinically significant, induce clinical signs or symptoms, require concomitant therapy or require changes in study treatment), should be recorded on the Adverse Events CRF.

Laboratory abnormalities, that do not meet the definition of an adverse event, should not be reported as adverse events. A Grade 3 or 4 event (severe) as per CTCAE does not automatically indicate a SAE unless it meets the definition of serious as defined below and/or as per investigator's discretion.

11.5.2 **Serious Adverse Event Reporting**

For the time period beginning at treatment allocation through **90** days following cessation of treatment, or **180** days following cessation of treatment if the subject initiates new anticancer therapy, whichever is earlier, any serious adverse event, or follow up to a serious adverse event, including death due to any cause whether or not related to the study drug, must be **submitted on an SAE form** and assessed by PI in order to determine reporting criteria to regulatory authorities, IRB, DSMC, FDA or Sponsor.

All SAEs will be followed until satisfactory resolution or until the site investigator deems the event to be chronic or the adherence to be stable. Other supporting documentation of the event may be requested by the study sponsor and should be provided as soon as possible. The study sponsor will be responsible for notifying FDA of any unexpected fatal or life-threatening suspected adverse reaction as soon as possible but in no case later than 7 calendar days after the sponsor's initial receipt of the information.

All subjects with serious adverse events must be followed up for outcome.

Any additional information for the SAE including complications, progression of the initial SAE, and recurrent episodes must be reported as follow-up to the original episode **within 24 hours** of the investigator receiving the follow-up information.

An SAE occurring at a different time interval or otherwise considered completely unrelated to a previously reported one should be reported separately as a new event.

Any SAEs experienced after the reporting period described above should only be reported to FDA/IRB if the investigator suspects a causal relationship to the study treatment.

Information about all SAEs is collected and recorded on the **Serious Adverse Event Report Form**; all applicable sections of the form must be completed in order to provide a clinically thorough report. The investigator must assess and record the relationship of each SAE to each specific study treatment (if there is more than one study treatment), complete the SAE Report Form, and submit the completed form.

Each reoccurrence, complication, or progression of the original event should be reported as a follow-up to that event regardless of when it occurs. The follow-up information should describe whether the event has resolved or continues, if and how it was treated, whether the blind was broken or not, and whether the patient continued or withdrew from study participation.

All SAE must be recorded on a MedWatch 3500 Form. SAE reports and any other relevant safety information are to be forwarded to the following

MedWatch 3500 Reporting Guidelines:

A copy of all 15 Day Reports and Annual Progress Reports is submitted as required by FDA. Investigators will cross reference this submission according to local regulations to the Investigational Compound Number (IND, CSA, etc.) at the time of submission.

An investigator who is a qualified physician will evaluate all adverse events according to the NCI Common Terminology for Adverse Events (CTCAE), version 5.0. Any adverse event which changes CTCAE grade over the course of a given episode will have each change of grade recorded on the adverse event case report forms/worksheets. All adverse events regardless of CTCAE grade must also be evaluated for seriousness.

Reporting Requirements for IND holder

For Investigator-sponsored IND studies, reporting requirements for the FDA apply in accordance with the guidance set forth in 21 CFR, Part 312.32. Events meeting the following criteria need to be submitted to the FDA as Expedited IND Safety Reports.

7 Calendar-Day Telephone or Fax Report

The Sponsor-Investigator is required to notify the FDA of a fatal or life-threatening adverse event that is unexpected and assessed by the investigator to be possibly related to the use of *investigational agents*. An unexpected adverse event is one that is not already described in the most recent Guidance for Investigator section of the Investigator's Brochure. Such reports are to be telephoned or faxed to the FDA, within 7 calendar days of the first learning of the event.

15 Calendar-Day Written Report

The Sponsor-Investigator is also required to notify the FDA and all participating investigators, in a written IND Safety Report, of any serious unexpected adverse event that is considered reasonably or possibly related to the use of investigational agent.

Written IND Safety Reports with analysis of similar events are to be submitted to the FDA, within 15 calendar days of first learning of the event. The FDA prefers these reports on a MedWatch 3500 Form but alternative formats (e.g., summary letter) are acceptable.

FDA Fax number of IND Safety Reports: [name].

[figure not shown]
The IND sponsor will also make an assessment of whether the event constitutes an unanticipated problem posing risks to subjects or others (UP). This assessment will be provided to the Emory University IRB, which, in turn will make a final determination. If the Emory IRB determines an event is a UP it will notify the appropriate regulatory agencies and institutional officials.

All Adverse Events will be reported to regulatory authorities, IRB/IECs and investigators in accordance with all applicable global laws and regulations.

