Objectives:	
Primary Objective: Compare the safety and accuracy/efficacy of low dose Y90 resin microspheres and MAA in predicting the actual dose delivered to the tumor, liver, and lung after Y90 therapy.
 
Secondary Objectives:
 
 1. Optimize low dose Y90 techniques in predicting TNR and LSF. 2. Identify tumor dose response thresholds (TDRT) and tumor dose distribution in patients with HCC treated with Y90 resin microspheres.
Endpoints:	
Primary Endpoint: The lung shunt fraction (LSF) and tumor to normal liver activity ration (TNR).
 
Secondary Endpoints:
 
 1. Monitoring all grades of Y90 related toxicity

	2. Tumor response evaluation at 1, 3 and 6 months and determination TDRT
Study Population:	N=30 patients with hepatocellular carcinoma (HCC), male or female, =>18 years of age, all ethnicities, ECOG <2, and generally local patients referred to Winship.
Phase:	2
Description of Sites/Facilities Enrolling Participants:	All patients will be recruited at Emory Interventional Radiology Clinics after they have been discussed and referred through multidisciplinary liver tumor boards. Only patients that are found to be ideal candidates for Y90 radioembolization at tumor boards will be considered for recruitment. Emory University Hospital and Emory University Hospital Midtown will be the clinical sites to perform the study.

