3. OBJECTIVES AND ENDPOINTS

OBJECTIVES	ENDPOINTS
Primary	
To compare the safety and accuracy/efficacy of low dose Y90 resin microspheres and MAA in predicting the actual dose delivered to the tumor, liver, and lung after Y90 therapy.	
 • Safety: adverse events related to Y90 radioembolization and angiography will be document by physical examination, clinical laboratory test and cross-sectional imaging. • Accuracy/Efficacy: The accuracy/efficacy of MAA as a predictor of therapeutic Y90 distribution will be compared to that of low-dose Y90.
Secondary	
 1. To Identify tumor dose response thresholds (TDRT) and tumor dose distribution in patients with HCC treated with Y90 resin microspheres. 2. To optimize low dose Y90 techniques in predicting TNR and LSF. 
 • Imaging Modified Response Criteria in Solid Tumors (m-RECIST) will be used on follow-up multiphase CT or MRI at 1, 3 and 6 months post Y90 radioembolization • Tumor dose response threshold will be determined • Imaging parameters for both Y90 SPECT and PET in both low and therapeutic dose will be optimized with the goal of recommending one of either SPECT or PET as the feasible imaging modality of choice at the conclusion of the study.

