3:00 PM-3:30 PM: Removal of the radial sheath at IR post procedural area and discharge.

4:30-5:30 PM: Y90 PET/CT at Cardiac PET center on the 4th floor of EUHM.

Patient is free to go home after this.

K. Y90 Therapy Tumor, Liver, and Lung Dose Calculation (Friday)

Utilizing the MIM software, post Y90 therapy PET/CT data and partition method described above, the mean actual dose delivered to the tumor, normal liver, and lung will be calculated by Drs. [name] and [name]. The software will generate ROIs from the inside to the periphery of the tumor based on Y90 delivery, and Dose Volume Histograms (DVH) plotting the delivered dose as a function of liver volume. Using DVH, % of tumor volume receiving >100Gy and dose range to the tumor will be also calculated.

L. Follow-up phone call [REDACTED] or study nurse (1-week post therapy)

Patient will be followed by phone to ensure they are doing well, and they will be screened for any symptoms related to adverse events. If any concerning symptoms is reported, they will be brought to IR clinic for further evaluation.

M. 1-Month clinical and Imaging Follow-up

- Multiphase liver mass protocol MRI or CT will be obtained
- Brief medical history
- Symptom-directed physical exam
- ECOG Performance Status
- Vitals signs
- Review of prior/concomitant medications
- Clinical laboratory tests for:
 - Hematology
 - CMP

N. 3-Month clinical and Imaging Follow-up

- Multiphase liver mass protocol MRI or CT will be obtained
- Brief medical history
- Symptom-directed physical exam
- ECOG Performance Status
- Vitals signs
- Review of prior/concomitant medications
- Clinical laboratory tests for:
 - Hematology
 - CMP

O. 6-Month clinical and Imaging Follow-up

- Multiphase liver mass protocol MRI or CT will be obtained
- Brief medical history
- Symptom-directed physical exam
- ECOG Performance Status

- Vitals signs
- Review of prior/concomitant medications
- Clinical laboratory tests for:
 - Hematology
 - CMP

End of Treatment

End of treatment is defined as the last planned Y90 therapy within the 6-month dosing period. For subjects who discontinue drug treatment prior to 6 months, end of treatment is considered the last visit where the decision is made to discontinue treatment. All required procedures may be completed within \pm 7 days of the end of treatment visit. Repeat disease assessment is not required if performed within 28 days prior to the end of treatment visit.

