10.5 Safety Analyses

Adverse event data will be described and graded per the NCI CTCAE 5.0 guidelines. For each adverse event, information to be collected includes event description, time of onset, clinician assessment of severity, relationship to study product (assessed only by those with the training and

authority to make a diagnosis), and time of resolution/stabilization of the event. Regardless of relationship, all AEs will be recorded with start dates occurring any time after patient receives Y90 until 7 (for non-serious AEs) or 100 days (for SAEs) after the last day of study participation. At each study visit, the investigator will inquire about the occurrence of AE/SAEs since the last visit. Events will be followed for outcome information until resolution or stabilization.

Any medical condition that is present at the time that the participant is screened will be considered as baseline and not reported as an AE. However, if the study participant's condition deteriorates at any time during the study, it will be recorded as an AE. Changes in the severity of an AE will be documented to allow an assessment of the duration of the event at each level of severity to be performed. AEs characterized as intermittent require documentation of onset and duration of each episode.

The maximum grade for each type of toxicity will be recorded for each patient, and frequency tables will be reviewed to determine toxicity patterns. Adverse events will be summarized and described within each cohort. They will initially be reviewed regardless of attribution, but also whether they are possibly, probably, or definitely related to treatment. In addition, we will review all adverse event data that are graded as 3, 4, or 5 and classified as either "unrelated" or "unlikely to be related" to study treatment in the event of an actual relationship developing. The incidence of severe adverse events or toxicities will be described. We will assess the proportion of patients who experience grade 3 or higher non-hematologic toxicity. To assess tolerability, we will also capture the proportion of patients who go off treatment due to adverse events.

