11.2 Definition of Adverse Events (AE)

Adverse event means any untoward medical occurrence associated with the use of an intervention in humans, whether or not considered intervention-related (21 CFR 312.32 (a)).

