The DSMC will render a recommendation and rating based on the overall trial conduct. The PI is responsible for ensuring that instances of egregious data insufficiencies are reported to the IRB. Continuing Review submissions will include the DSMC recommendation letter. Should any revisions be made to the protocol-specific monitoring plan after initial DSMC approval, the PI will be responsible for notifying the DSMC of such changes. The Committee reserves the right to conduct additional audits if necessary.

The projected recruitment is 1 patient per week. As such, in order to assure data integrity and protocol adherence, the data will be analyzed every 1 month or after recruitment of 4 new patients. The adverse events will be recorded on an ongoing as dictated by patient follow-up schedule outlines above. As per agreement with SIRTEX, all grades of AE's related to Y90 RE will be recorded based CTCAE guideline. All adverse reactions will also be recorded. Grades 4 and 5 related to Y90 radioembolization will be reported to both Winship DSMC and FDA. All grades of AE's and adverse reactions will be reported to DSMC every 6 months.

The oversight of the study will be performed by [name] and [name] during monthly research study meetings with the core study group members. Prior to the meeting, the adherence to protocol and data collection in each individual patient will be confirmed by [name] or [name]. The study team members will undergo regular training and review sessions to ensure complete adherence to the protocol. Prior to commencement of the study, all study team

members will undergo mandatory training outlining the protocol and patient recruitment strategies for 2 hours. The study team will then undergo regular monthly research progress meeting to ensure adherence to the protocol and appropriate data collection and reporting.

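### The laboratory AE rule in Section 11.5.1 can lead the all-grades Y90 toxicity tables to under-count asymptomatic, untreated laboratory changes, because no planned analysis grades the scheduled blood results themselves

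*Combined protocol and SAP*

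**What the plan says.** **Endpoint.** The synopsis (1.1) gives as a secondary endpoint "Monitoring all grades of Y90 related toxicity". Section 3 also places safety under the primary objective, with adverse events that "will be document by physical examination, clinical laboratory test and cross-sectional imaging". Section 13.2 adds that "all grades of AE's related to Y90 RE will be recorded based CTCAE guideline".

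**Entry rule.** Section 11.2 is broad: "Adverse event means any untoward medical occurrence associated with the use of an intervention in humans", whether or not judged related. Section 11.5.1 is narrower for laboratory findings. They are AEs in their own right if they "are considered clinically significant, induce clinical signs or symptoms, require concomitant therapy or require changes in study treatment". It then says: "Laboratory abnormalities, that do not meet the definition of an adverse event, should not be reported as adverse events".

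**Analysis.** Section 10.5 describes adverse event data graded by CTCAE 5.0: "The maximum grade for each type of toxicity will be recorded for each patient, and frequency tables will be reviewed". It also plans the proportion of patients with grade 3 or higher non-hematologic toxicity. Section 10.3 promises summary statistics for all variables, with mean, standard deviation and range for continuous ones.

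**Samples.** The schedule in 1.3 marks blood sampling at screening and at 1, 3 and 6 months. Section 8.1 lists hematology and CMP at those visits and on mapping day, where tests need not be repeated if screening was within the previous 7 days.

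**The concern.** An all-grades toxicity endpoint should pick up low-grade findings, and in a study of liver-directed radiation many of these would be laboratory values: bilirubin, transaminases, albumin, platelets. The synopsis names limiting liver toxicity as part of the study's purpose. If such a change produces no symptoms and is not treated, the plan leaves its appearance in the tables to a judgement for which it gives no threshold. Two investigators could then produce different toxicity tables from the same blood results.

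Eligibility makes this harder to read. Section 5.1 admits bilirubin up to 2 mg/dL, albumin down to 3 g/dL, AST/ALT up to 3 times the upper limit of normal, and platelets just above 50,000/mcL. Some patients will start with abnormal values, so laboratory toxicity can be interpreted only as a change from each patient's own baseline. No planned table shows that change.

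**Working it through.** The plan gives no figure to reproduce here. The check is mainly a comparison of sections.

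**Step 1: routes open to an asymptomatic, untreated change.**
- Signs or symptoms: closed by definition.
- Concomitant therapy: closed by definition.
- Change in study treatment: narrow but not closed. Section 7.4.1 foresees normally one treatment, and most follow-up blood is drawn after it. The same section also provides for a second session at 4 weeks if eligibility is maintained, and eligibility includes laboratory limits.
- Clinical significance: open, by investigator judgement. Section 11.5.1 sets no grade above which a value must be recorded, so even a grade 3 value without symptoms or treatment is left to judgement.

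**Step 2: does another section recover the value as a graded toxicity?**
- 10.5 tabulates adverse event data and so inherits the filter.
- 13.2 promises all grades of AEs. A value that 11.5.1 excludes has not become an AE. The instruction in 11.5.2 to record each change of CTCAE grade has the same limit.
- 8.2 requires a baseline grade for history and examination findings. It does not name laboratory values.
- 10.3 would summarise laboratory values by mean, standard deviation and range. This shows no grades and no individual shifts, and a group mean can conceal a few patients with marked change.

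No section supplies laboratory grades independently of AE entry.

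**Step 3: direction.** Compared with grading the same scheduled values directly, the filter can remove patients from the count but cannot add any. The error, if there is one, is downward.

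**Step 4: illustration of size, on assumptions only.** Let p be the true proportion of patients with a graded, asymptomatic, untreated laboratory change, and c the share of them recorded as AEs. The documents give neither. With N = 30 (synopsis):

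expected patients recorded = 30 × p × c; chance of recording at least one = 1 − (1 − p × c)^30.

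| Assumed p | c = 100% | c = 50% | c = 25% |
|---|---|---|---|
| 10% | 3.0 (95.8%) | 1.5 (78.5%) | 0.75 (53.2%) |
| 30% | 9.0 (>99.9%) | 4.5 (99.2%) | 2.25 (90.4%) |
| 50% | 15.0 (>99.9%) | 7.5 (>99.9%) | 3.75 (98.2%) |

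Worked cell: p = 10%, c = 25% gives 30 × 0.10 × 0.25 = 0.75 and 1 − 0.975^30 = 0.532. If capture is complete (c = 100%), nothing is lost.

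**Step 5: a related gap.** Section 11.5.1 ends AE recording 90 days after cessation of treatment. Section 10.5 runs it to 7 days after the last day of participation for non-serious events. Under the first rule, a change first seen in the 6-month blood falls outside the AE window; under the second it falls inside. The two need reconciling.

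**The case against.** The strongest reply is that the sections fit together. On this view 11.5.1 defines what counts as an AE, and the synopsis and 13.2 then say that all Y90-related AEs are graded with no minimum grade. All grades need not mean every out-of-range value. Several sections also look toward change: 11.5.1 names laboratory tests as a way AEs may be detected, 10.5 records deterioration of a baseline condition as an AE, and 8.2 treats increased severity of a pre-existing condition as one. The definition in 11.2 has no significance condition, so a generous reader could admit most laboratory worsening.

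Much of this stands. The wording does allow that reading, and change from baseline is not ignored in principle. What it does not supply is a rule that gives the same answer whoever applies it, or a table of graded laboratory change. The broad definition in 11.2 and the specific laboratory criteria in 11.5.1 point different ways, and site staff are likely to follow the specific one.

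Three further objections also stand:
- The endpoint concerns Y90-related toxicity. Program-derived grades carry no attribution, and cirrhosis, progression and later therapies (allowed after progression at 3 months) also move these values. Substituting them into the endpoint would change it.
- Safety is descriptive in a single-arm study, so no between-arm comparison is biased.
- The loss probably falls mainly on grades 1 and 2, whereas the one grade-specific proportion named in 10.5 is grade 3 or higher non-hematologic toxicity.

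**Conclusion.** The point holds in a limited form. The toxicity tables, and with them the all-grades secondary endpoint, can under-count asymptomatic, untreated laboratory changes. The direction is downward; the size is unknown. The table of assumed values shows only that, with 30 patients, modest non-capture could remove several patients from a count or leave an uncommon change unrecorded.

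A reader might infer more than the documents support:
- That clinical significance is the only way in. It is one of four alternatives, and is the main route only for changes without symptoms or treatment.
- That under-counting is established. The plan gives no toxicity rate and no capture rate, and a careful investigator could record every such change.
- That the laboratory data are lost. They are collected and fall under the general summaries; what is missing is grading and individual shift.

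The sponsor should make this change because it is cheap and gives the safety report a component that does not depend on judgement. The LSF and TNR comparisons are unaffected.

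**What to change.** Leave the laboratory rule in 11.5.1 in force for AE and SAE reporting. Add one paragraph to 10.5:

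- CTCAE v5.0 grades will be derived by program from all scheduled hematology and CMP results: screening, mapping day where drawn, and 1, 3 and 6 months.
- Baseline is the last value before the first Y90 administration.
- For all treated patients, worst post-baseline grade and shift from baseline will be reported per analyte, whether or not an AE was entered.
- This table stands beside the Y90-related AE table and does not replace it. A note will say that the grades carry no attribution and that cirrhosis, progression and later therapies also contribute.

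Reconcile the AE recording windows in 10.5 and 11.5.1 at the same time.

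The cost is one paragraph, some programming and one extra table, with no added samples or visits. The drawback is that more low-grade laboratory change will be shown, some of it not due to Y90.
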